8.4. Pharmacogenomics

All subjects participating in the study will have the option to participate in blood sampling for pharmacogenomics and this will be consented to collect this optional test. Subjects who do not wish to participate in the pharmacogenomic sampling may still participate in the study.

on Day 14 visit, but may be collected at any time during the study or at a separate post study visit, if necessary, as shown in the SoA (Table 3). separate procedure manual.

participants.

investigator and

9. STATISTICAL CONSIDERATIONS

Unless specified otherwise, efficacy measures will be summarized by planned (i.e., randomized) treatment and based on the FAS population, and safety measures will be summarized by actual treatment received and based on the Safety population. All efficacy endpoint analyses will be performed on eyes enrolled in the study (referred to as study eyes). Safety assessments that pertain to the eye will be analyzed by the study eye and fellow eye separately. Safety assessments that pertain to the subject will be analyzed at the subject level.

Continuous variables will be summarized using descriptive statistics such as number of observations (n), mean, standard deviation, medium, minimum, and maximum. Categorical variables will be tabulated using frequency (n) and percent (%).

Statistical testing is planned for the analysis of efficacy endpoints of the double-masked period only (not safety endpoints) and will assess for superiority of efficacy observed in the test arm (440 μ g DE-109 every 2 months) compared to the sham control. Statistical testing will not involve the dummy arm, which is included in the study to help ensure masking of treatment assignments. Unless specified otherwise, the statistical testing will be conducted at a significance level of 0.05 (two-sided). Additional details of the statistical methods will be described in the Statistical Analysis Plan (SAP).

All data manipulations, descriptive summaries, and statistical hypothesis testing will be performed using SAS Version 9.4 or later. FDA guidance regarding case report tabulations (annotated eCRFs, SAS datasets, metadata, and SAS programs) in electronic submissions will be followed. Data definition tables will be created for SDTM and ADaM datasets separately.

9.1. Estimands

- The **primary estimand** is: Vitreous haze 0 (VH0) response rate in DE-109 440 µg group vs. Sham group at Month 5 in all study eyes that received at least one dose of the study treatment where all eyes that were rescued due to worsening of uveitis or discontinued from the study due to lack of efficacy or due to adverse event before Month 5 will be treated as non-responders. For study eyes that were rescued for any other reasons or had missing data due to other reasons, imputation by the multiple imputation-based approach will be used.
- The **treatment policy estimand** is: VH0 response rate in DE-109 440 µg group vs. Sham group at Month 5 in all study eyes that received at least one dose of the study treatment regardless of whether subjects have received rescue therapy or discontinued from the study due to lack of efficacy or due to adverse event. For study eyes that had missing data due to any reason, imputation by the multiple imputation-based approach will be used.
- The **composite estimand** is: Mean composite score in DE-109 440 µg group vs. Sham group at Month 3 and at Month 5 in all study eyes that received at least one dose of study treatment. Each study eye will be assigned one of the following scores:
 - Score = 3 if a study eye achieved VH score of 0 at the specified visit without taking any rescue therapies that could affect VH score prior to the specified visit
 - Score = 2 if a study eye had at least improved by 2 units in VH (compared to baseline) at the specified visit without taking any rescue therapies that could affect VH score prior to the specified visit

- \circ Score = 1 if a study eye achieved VH score of 0.5+ at the specified visit without taking any rescue therapies that could affect VH score prior to the specified visit
- Score = -1 if a study eye got rescued due to worsening of uveitis or discontinued from the study due to lack of efficacy or due to adverse event prior to the specified visit
 Score = 0 if otherwise

9.2. Statistical Hypotheses

The primary efficacy endpoint (VH 0 response at Month 5) will be analyzed using the Cochran-Mantel-Haenszel (CMH) test with Row Mean Scores statistic, stratified by the number of enrolled eyes from a subject (one eye or two eyes), baseline systemic (oral) corticosteroid use (yes or no), and region (US or non-US). The null (H₀) and alternative (H₁) hypotheses are as follows:

$$H_0: \pi_{sham} = \pi_{440}$$
$$H_1: \pi_{sham} \neq \pi_{440}$$

where π_{sham} and π_{440} denote the response rate for sham and 440 µg DE-109, respectively.

9.3. Sample Size Determination

Assuming a 30% VH 0 response rate for DE-109 440 μ g group and a 12% response rate for the sham treatment group, 160 subjects (80 subjects per arm) is required to achieve 80% power to detect such a difference in response rate between the DE-109 440 μ g group and the sham treatment group using the Pearson's Chi-square test (two-sided, $\alpha = 0.05$). Including approximately 40 subjects in the dummy arm, a total of approximately 200 subjects with active NIU-PS will be randomized in a 2:2:1 ratio to DE-109 440 μ g, sham, and dummy arms.

9.4. **Populations for Analyses**

The following analysis populations for study analyses are defined: Full Analysis Set (FAS), Safety, Per-Protocol (PP), Intent-to-Taper, Macular Edema, Vision 20/40 or Worse:

- The **FAS population** will consist of all study eyes that are randomized and received at least one administration of study treatment. The FAS population will be the analysis population for the primary analysis and will use treatment as randomized.
- For analyses of ocular AEs and safety parameters assessed per eye, the **Safety population** will consist of all study eyes which received at least one administration of IP. For analyses of non-ocular AEs and safety parameters assessed per subject, the **Safety population** will consist of all subjects who received at least one administration of IP.
- The **PP population** will be a subset of the FAS population. The PP population will be the analysis population for sensitivity analyses and will use treatment as randomized. Any study eye affected by a significant protocol deviation (such that the outcome to treatment could be altered) will be excluded from the PP population. In addition, any study eye without the Month 5 VH score will be excluded from the PP population. Eyes to be excluded from the PP population will be identified before the unmasking of treatment assignments.

- The Intent-to-Taper population will be a subset of the FAS population, consisting of study eyes from subjects who were taking systemic (oral) corticosteroids at a stable prednisone-equivalent dose between ≥15 mg/day and ≤40 mg/day for at least 1 week (7 days) prior to and including on Day 1. The Intent-to-Taper population will be used for the analysis of tapering success performed using eyes as randomized.
- The Macular Edema population will be a subset of the FAS population and will consist of study eyes with $CST \ge 300$ microns at baseline.
- The Vision 20/40 or Worse population will be a subset of the FAS population and will consist of study eyes with BCVA ≤ 70 ETDRS letters (Snellen equivalent of 20/40 or worse) at baseline.

9.5. Statistical Analyses

Details of statistical analyses will be described in the SAP, which will be developed and finalized before database lock. This section is a summary of the planned statistical analyses of the primary and secondary endpoints (see Table 4).

9.5.1. Handling of Missing Values

In the analysis of VH 0, VH 0 or 2-unit decrease (improvement), and VH 0 or 0.5+ responses:

- Subjects who (a) receive rescue therapy for conditions other than worsening of uveitis or (b) are rescued due to the worsening of uveitis but do not meet the protocol-defined rescue criteria, missing VH scores subsequent to receiving rescue therapy will be imputed using a multiple imputation-based approach before receiving rescue therapy.
- Missing VH scores of subjects not rescued before Month 5/Month 3 visit will be imputed using a multiple imputation-based approach.

The multiple imputation model will include vitreous haze measures at preceding visits and baseline characteristics. The response status will then be determined based on the observed or imputed VH scores.

No imputation is needed for composite score analysis as eyes with missing VH scores will be assigned a score of zero, unless they are rescued due to the worsening of uveitis or discontinued from the study due to lack of efficacy or adverse event (which will be assigned with a score of -1).

For medical events including AEs, completely or partially missing onset and resolution dates will be imputed in a conservative fashion to be detailed in the SAP. The same rules will be followed to impute completely or partially missing start and end dates of non-study medications.

Unless specified otherwise, descriptive summaries will be based on observed cases. No imputation of missing scores will be implemented.

Additional details on handling of missing data and sensitivity analyses on imputation methods will be provided in the SAP.

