The primary efficacy endpoint is defined as a VH score of 0 (resolution of inflammation) at Month 5; a VH score of 0 at Month 3, composite score at Month 3 and at Month 5 are key secondary efficacy endpoints. Month 5 (one month after the Month 4 injection) and Month 3 (one month after the Month 2 injection) were selected as pre-specified endpoints for evaluating VH based on tissue distribution studies which demonstrated that peak levels of sirolimus are maintained at the target tissue for up to two months after intravitreal injection of DE-109.

Secondary efficacy assessments include benefit as measured by the ability to taper from corticosteroids and achieve resolution of VH, which is evaluated in the subgroup of subjects receiving systemic (oral) corticosteroids at baseline. Accordingly, to help ensure balance across the treatment arms within this subgroup, the study randomization will be stratified by subject's

systemic (oral) corticosteroid use at baseline (yes/no) as well as the number of eyes enrolled (one eye or two eyes) and region (US or non-US).

In this study which includes a sham control during the double-masked period, rescue therapy is allowed for subjects who experience worsening of disease or vision per protocol-specified criteria, or at the investigator's judgement. In the analysis of VH endpoints including the primary endpoint, the use of rescue therapy prior to the evaluation of a VH endpoint will be accounted for by considering the subject to be a non-responder.

An independent Data Monitoring Committee (DMC) will periodically review unmasked aggregated and individual-level data during the conduct of the trial to help ensure safety and data integrity. An independent statistical and programming team will be used to perform these interim analyses of unmasked data.

Use of the 6-month, single-arm, open-label period after completion of the 6-month doublemasked, controlled period allows the evaluation of the efficacy and safety of intravitreal injection of DE-109 440 μ g every 2 months for longer duration than appropriate for a placebo or sham control.

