5.2. Handling of Missing Data

5.2.1. Efficacy Measures

For the analysis of VH 0 response at Month 5 (primary endpoint) and at Month 3 (key secondary endpoint), study eyes will be treated as non-responders if they meet at least one of the following criteria:

- 1. A study eye is rescued due to the protocol-specified worsening of uveitis (Section 8.1.6)
- 2. A subject discontinued from the study due to lack of efficacy or adverse events
- 3. A study eye meets the protocol-specified worsening of uveitis rescue criteria (Section 8.1.6) regardless whether the eye received any rescue therapies

Study eyes which were rescued due to worsening of uveitis specified under previous protocol versions but did not meet the rescue criteria under the current version will be treated as rescued due to other reasons and censored the data after being rescued. The multiple imputation-based approach (Section 8.2.1) will be applied to impute missing VH score data of study eyes which

were not rescued and treated as non-responders. The VH 0 response status will then be determined based on the observed or imputed VH score.

The same approach will be applied to the inferential analyses of other VH response endpoints.

For the analysis of composite score (at Month 3 and at Month 5), study eyes with missing VH score at a given visit will be assigned with a score of 0, unless the study eyes got rescued due to protocol-specified worsening of uveitis or corresponding subjects discontinued the study due to adverse events or lack of efficacy (in this case, the score will be -1).

For the analysis of corticosteroid tapering success on the Intent-to-Taper population, study eyes rescued before Month 5/Month 3 will be treated as corticosteroid tapering failures. The Last-Observed-Carried-Forward (LOCF) approach will be applied to impute missing data of study eyes not rescued before Month 5/Month 3, i.e., the missing overall prednisone-equivalent dose at Month 5/Month 3 will be imputed by last derived overall dose. The tapering status at Month 5/Month 3 will then be determined based on the derived or imputed overall dose.

No imputation is needed for the analysis of the binary endpoint "use of rescue therapy before Month 5/Month 3".

To assess the impact of missing data on the primary analysis results for VH 0 response at Month 5, the following imputation approaches will be applied to some sensitivity analyses:

- The LOCF approach for any FAS study eyes with missing VH score at Month 5

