- Treatment policy approach: The primary analysis will be performed on FAS study eyes regardless whether they get rescued. That is, no censoring of observed VH score after a rescue will be implemented. Other missing VH scores will be imputed with multiple imputation-based approach.

For analyses of "change from baseline in central subfield thickness at Month 5 as measured by OCT" and "change from baseline in the NEI VFQ-25 composite score at Month 5", the LOCF approach will be applied for any FAS study eyes with missing score at Month 5.

"Change from baseline in VH score at post-baseline visits up to Month 6" and "change from baseline in BCVA at post-baseline up to Month 6" will be analyzed using the mixed-effects model for repeated measures (MMRM) on observed cases. No imputation of missing data will be needed.

Subgroup analyses of all binary endpoints will employ the same imputation approach for the primary analysis of that endpoint. Other descriptive efficacy summaries will be based on observed data, unless otherwise specified.

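### Conflicting primary-endpoint rules for eyes rescued without meeting a protocol criterion; the SAP does not expressly discard VH scores observed after such a rescue

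*Protocol*

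**What the plan says.** Protocol 6.5.6 allows rescue at the investigator's discretion when none of the three criteria is satisfied, and SAP 8.1.6 pools these cases as an Other category. A rescued subject can stay in the study and have an observed Month 5 VH score. The sections that decide how that eye counts are these.

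- **Protocol 9.5.1** covers two groups: (a) rescue for a condition other than worsening of uveitis, and (b) rescue for worsening with no criterion met. For both, "missing VH scores subsequent to receiving rescue therapy will be imputed using a multiple imputation-based approach before receiving rescue therapy". Response status then comes from the observed or imputed scores. The end of the quoted clause does not parse.
- **Protocol 9.5.2** fails subjects who met a criterion, whether or not they were rescued.
- **Primary estimand (Protocol 9.1, SAP 2.2.1)** fails all eyes rescued due to worsening, without requiring that a criterion was met. The remaining eyes go to imputation: "For study eyes that were rescued for any other reasons or had missing data due to other reasons, imputation by the multiple imputation-based approach".
- **Protocol 4.2** says that "the use of rescue therapy prior to the evaluation of a VH endpoint will be accounted for by considering the subject to be a non-responder".
- **SAP 5.2.1 and 8.2.1** fail eyes with protocol-specified worsening. Eyes rescued under an earlier protocol version that miss the current criteria "will be treated as rescued due to other reasons and censored the data after being rescued".
- **SAP 5.2.1, treatment-policy analysis**, specifies that "no censoring of observed VH score after a rescue will be implemented".

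**The concern.** The same eye can be a responder, an imputed value or a failure, depending on the section the programmer follows. Under the literal Protocol 9.5.1 rule, the effect of the rescue drug is credited to the randomised arm. The primary analysis would then be partly a treatment-policy analysis, which the plan keeps as a separate sensitivity analysis. If sham eyes are rescued more often, which is plausible but not stated, the sham rate rises more than the DE-109 rate and the difference shrinks.

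The literal rule also clashes with the first key secondary endpoint. The composite gives its top score only for VH 0 reached without rescue therapy that could affect VH, so an eye could be a primary responder and be denied that score. The primary test gates the whole hierarchy, so the choice should not be left to programming or to a decision after unmasking.

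**Working it through.** **Text comparison.** Take an eye rescued before Month 5, no criterion met, with VH 0 observed at Month 5.

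| Source | Group (a): rescue not for worsening | Group (b): rescue for worsening, no criterion met |
|---|---|---|
| Protocol 9.5.1, literal | responder (observed score used) | responder (observed score used) |
| Primary estimand | imputed | non-responder |
| Protocol 4.2 | non-responder | non-responder |
| SAP 5.2.1 and 8.2.1 | not a failure; discarding the observed score not expressly stated | same as (a) |

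The SAP's censoring sentence names only earlier-version rescues. Its imputation sentences refer to missing scores. No sentence sets an observed post-rescue score to missing for a current-version Other rescue in the primary analysis. SAP 8.2.2 (GEE) and 8.2.4.2 (MMRM) do state such an exclusion.

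**Plan's figure.** Protocol 9.3: "Assuming a 30% VH 0 response rate for DE-109", "a 12% response rate for the sham treatment group", and "160 subjects (80 subjects per arm) is required to achieve 80% power" (Pearson chi-square, two-sided 0.05). With d the difference in rates and p̄ their mean, power = Φ[(d − 1.96·SE0)/SE1], where SE0 = √(2p̄(1−p̄)/n) and SE1 = √((p1(1−p1)+p2(1−p2))/n). For 0.12 and 0.30 with n = 80, SE0 = 0.0644 and SE1 = 0.0628. Power = Φ[(0.18 − 0.1262)/0.0628] = 0.804, so the figure reproduces.

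**Illustration on assumed rates.** Let r be the proportion of an arm rescued off-criterion and q the proportion of those with VH 0 afterwards. Take 12% and 30% as the rates under imputation. Counting observed scores gives p(1−r) + qr; failing the eyes gives p(1−r).

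- r = 10% sham, 5% DE-109, q = 30%: sham 0.12×0.90 + 0.30×0.10 = 13.8%; DE-109 0.30×0.95 + 0.30×0.05 = 30.0%. Difference 16.2 points, power 0.70.
- Same r, q = 50%: 15.8% and 31.0%. Difference 15.2 points, power 0.62.
- Same r, all such eyes failed: 10.8% and 28.5%, power 0.81.
- r = 5% in both arms, q = 30% to 50%: difference 17.1 points, power 0.755 to 0.741.
- r = 2% in both arms, same q: power about 0.78.
- r = 5% sham, 10% DE-109, q = 50%: 13.9% and 32.0%, power 0.78.

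**Other anchor.** If 12% and 30% are instead the rates when all such eyes fail, 10%/5% rescue with observed scores counted gives 14.0% vs 31.0% (power 0.735) at q = 20% and 18.0% vs 33.0% (0.587) at q = 60%. The direction is the same; the size differs.

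**The case against.** The strongest reply is that the SAP largely settles the matter. Protocol 9.5 calls itself a summary and leaves missing-data detail to the SAP. Placing earlier-version rescues in an other-reasons class and censoring them presupposes that the class is censored. Defining the treatment-policy analysis by the absence of censoring has little point unless the primary analysis censors, and the GEE and MMRM rules drop post-rescue scores. This stands as evidence of intent. It does not supply the missing instruction, because the only explicit censoring sentence in the primary analysis covers a narrower group.

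Protocol 4.2 is design rationale, and the analysis sections do not fail every rescue. That lowers its weight, but its sentence is about analysis and contradicts them.

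A reader might infer that the estimand imputes every eye rescued without meeting a criterion. It does not. Its worsening clause carries no criterion, so group (b) fails on its words. Telling the team simply to follow the estimand would therefore leave Protocol 9.5.1 and the SAP in conflict with it for group (b).

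The power figures rest on assumed rates, and nothing in the documents shows that sham eyes will be rescued off-criterion more often. For group (a) in particular an imbalance between arms is not evident. This stands in full.

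**Conclusion.** The concern holds as an incomplete and inconsistent rule that should be corrected before unmasking. Following the written text can count a VH 0 reached on rescue therapy as a primary response, and group (b) is handled differently in the estimand, Protocol 9.5.1 and the SAP.

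A reader might conclude that the plan has adopted a rule of crediting on-rescue responses. The documents do not support that: no SAP passage says such scores count in the primary analysis, and several point the other way.

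The size cannot be derived from the documents. A power of 0.70 to 0.62 needs twice as much off-criterion rescue on sham as on DE-109 (10% against 5%), 30% to 50% at VH 0 afterwards, one eye per subject, an unstratified test, and the planning rates read as those under imputation. With equal or lower rescue rates the loss is a few points. In these scenarios the consequence is lost power and a blurred estimand; they show no inflated false-positive risk.

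**What to change.** Before unmasking:

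1. In SAP 5.2.1 and 8.2.1, extend the censoring sentence to every study eye that starts rescue therapy before the visit and is not already a non-responder. All its VH scores after the rescue start date, observed or missing, are set to missing and imputed, whichever protocol version was in force.
2. In Protocol 9.5.1, make the imputation rule cover all post-rescue VH scores, observed or missing, and rewrite the end of the clause, which at present seems to place the imputation before the rescue.
3. State how group (b) is handled, and make Protocol 9.1, SAP 2.2.1, Protocol 9.5.1 and SAP 5.2.1/8.2.1 agree. Either limit the estimand's worsening clause to protocol-specified worsening, so that group (b) is imputed, or treat group (b) as non-responders throughout and widen the SAP's failure list to match.
4. Align the Protocol 4.2 sentence with the resulting rule.

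The cost is wording in two documents and slightly more imputed values. No new data are needed.

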9.5.2. Efficacy Analyses

Rescue therapy is defined in Section 6.5.6 and is essentially any treatment that would have a therapeutic effect on NIU-PS other than intravitreal DE-109. Rescue therapy is permitted in the case of worsening of uveitis that satisfies protocol-defined rescue criteria. The use of rescue therapy is considered in assessing the VH response endpoints (VH 0 response, VH 0 or 2-unit improvement, and VH 0 or 0.5+ response). In the analysis of these endpoints at a specific follow-up visit (e.g., Month 5 or Month 3), subjects who met one of the protocol-defined rescue criteria will be assessed as non-responders regardless of whether the subjects were rescued or not.

Endpoint	Statistical Analysis Methods
Primary endpoint: VH 0 response ^a at Month 5	For the primary analysis of VH 0 response at Month 5, the Cochran-Mantel-Haenszel (CMH) test with Row Mean Scores statistic stratified by number of enrolled eyes from a subject (one eye or two eyes), baseline systemic (oral) corticosteroid use (yes or no), and region (US or non-US) will be conducted. Logistic generalized estimating equation (GEE) model, treatment policy strategy, last-observation-carried- forward (LOCF) imputation, and multiple imputation with tipping point analysis will be used as a sensitivity analysis.
 Secondary endpoints: Key secondary efficacy endpoints: Composite endpoint^b at Month 5 VH 0 response at Month 3 Composite endpoint at Month 3 	A hierarchical approach will be used to control the overall Type I error rate associated with the multiple comparisons across the primary and the key secondary efficacy endpoints. If the hypothesis testing for the primary endpoint successfully rejects the null hypothesis, the first key secondary efficacy endpoint will be tested, and so on. All the other secondary efficacy endpoints are supportive in nature. Therefore, no formal hypothesis testing will be performed on secondary efficacy endpoints. Two-sided 95% confidence intervals and nominal p-values may be reported for them, and such results will be interpreted descriptively in terms of the support they provide to the treatment comparisons for the primary and the key secondary efficacy endpoints in the sense of logical consistency.

Table 8:Endpoint Statistical A	Analysis
--------------------------------	----------

Endpoint	Statistical Analysis Methods	
Other secondary efficacy endpoints (double-masked period of study):	For secondary efficacy endpoints during double- masked period:	

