8.2.1. Primary Analyses

The primary efficacy endpoint, VH 0 response, is defined as having a VH score of 0 at Month 5 (modified SUN scale). For the primary endpoint, the VH 0 response rate will be evaluated in accordance with the following null (versus alternative) hypothesis:

$$H_0: \pi_{sham} = \pi_{440}$$
versus

$$H_A: \pi_{sham} \neq \pi_{440}$$

where π_{sham} and π_{440} denote the response rate for sham and 440 µg DE-109, respectively.

The Cochran-Mantel-Haenszel (CMH) test with Row Mean Scores statistic (Yu et al., 2020), stratified by pooled strata based on the number of enrolled eyes from a subject (one eye or two eyes), baseline systemic (oral) corticosteroid use (yes or no), and region (US or non-US). Such pooling is needed to avoid the situation where subjects in too small strata might all have the same responses (either success or failure); hence, do not contribute to the test. To guarantee that

a pooled stratum has at least one success and one failure, the pooling algorithm will be performed as follows:

- Determine the number of subjects in each stratum, defined by crossing the number of enrolled eyes, baseline systemic corticosteroid use, and region.
- Within each combination of number of enrolled eyes and region, if one or both strata, stratified by corticosteroid use, have less than 25 subjects, then those strata will be pooled.
- Within each stratification factor level based on number of enrolled eyes, if at least one of (pooled/unpooled) strata have less than 25 subjects, then those strata will be pooled together.

The pooling algorithm will be performed based on the available data prior to the unmasking of the randomization. At the interim analysis, only number of enrolled eyes will be used as the stratification factor.

Study eyes will be treated as non-responders if they meet at least one of the following criteria:

- 1. A study eye is rescued due to the protocol-specified worsening of uveitis (Section 8.1.6)
- 2. A subject discontinued from the study due to lack of efficacy or adverse events
- 3. A study eye meets the protocol-specified worsening of uveitis rescue criteria (Section 8.1.6) regardless whether the eye received any rescue therapies

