Study eyes which were rescued due to worsening of uveitis specified under previous protocol version but did not meet the rescue criteria under the current version will be treated as rescued due to other reason and censored the data after being rescued. The multiple imputation-based approach will be applied to impute missing VH score data of study eyes which were not rescued and treated as non-responders. The VH 0 response status will then be determined based on the observed or imputed VH score.

For missing VH score due to any other reasons other than protocol-specified worsening of uveitis, the multiple imputation approach will be applied as follows:

- 1. Use Markov chain Monte Carlo (MCMC) to create monotone missingness first with VH score on the logarithm scale. Then obtain standard multiple imputations under MAR assumptions for missing VH scores using monotone regression on the logarithm scale. The imputed values will be then converted into an eligible VH score based on the absolute distance. The missing data are filled in and 50 complete datasets are created. The seed that will be used in the SAS program is 135711.
- 2. Each of 50 complete datasets will then be analyzed separately. The CMH test statistic, response rate for each treatment group, and the rate difference will be calculated for each complete sets.
- 3. The final CMH test statistic, obtained from each complete dataset, will be transformed using Wilson-Hilferty transformation and combined for inference purposes (O'Kelly et al., 2014). Rates and rate differences will also be combined without any transformations.

The Mantel-Haenszel weighted response rate (%) of each treatment group, the Mantel-Haenszel weighted rate difference, the corresponding asymptotic 95% confidence interval (CI) and the CMH's p-value will be reported.

The main part of the SAS code for the specified CMH test procedure and the multiple imputation are provided in Appendix C, respectively.

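### Protocol 9.5.1, read literally, multiply imputes unrescued subjects who left for lack of efficacy or an adverse event, contrary to the primary estimand; the SAP largely but not cleanly closes the gap

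*Protocol*

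**What the plan says.** **Protocol 9.1.** Under the primary estimand, eyes that "discontinued from the study due to lack of efficacy or due to adverse event before Month 5 will be treated as non-responders". Multiple imputation is kept for rescue or missing data for other reasons. SAP 2.2.1 says the same.

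**Protocol 9.5.1, VH response endpoints.** The second bullet says: "Missing VH scores of subjects not rescued before Month 5/Month 3 visit will be imputed using a multiple imputation-based approach". Response is then read off the completed data: "The response status will then be determined based on the observed or imputed VH scores". The reason for discontinuation plays no part.

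**Protocol 9.5.1, composite score.** Here the same discontinuations are singled out; the exception covers eyes "discontinued from the study due to lack of efficacy or adverse event (which will be assigned with a score of -1").

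**Protocol 9.5.2.** A failure rule is added for one group only: "subjects who met one of the protocol-defined rescue criteria will be assessed as non-responders regardless of whether the subjects were rescued or not".

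**Protocol 9.5.** The section describes itself as a summary: "Details of statistical analyses will be described in the SAP, which will be developed and finalized before database lock".

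**SAP 5.2.1 and 8.2.1.** Both list three criteria, any one of which makes an eye a non-responder. The second is: "A subject discontinued from the study due to lack of efficacy or adverse events". SAP 5.2.1 covers Month 5 and Month 3 and extends the approach to the inferential analyses of the other VH response endpoints.

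**SAP 8.2.1, after the criteria.** One sentence defines the eyes to be imputed by two conditions, rescue and non-responder status, with a single negation in front of the first. The steps then open with: "For missing VH score due to any other reasons other than protocol-specified worsening of uveitis, the multiple imputation approach will be applied as follows".

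**The concern.** Two rules in the protocol give different answers for the same eye on the primary endpoint. Take an eye whose subject leaves at Month 3 for an adverse event, unrescued and without meeting a rescue criterion. Protocol 9.1 makes it a failure at Month 5. The 9.5.1 bullet imputes its Month 5 score and lets it be a VH 0 responder. In the first key secondary endpoint that eye scores -1, the worst value on the scale.

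The SAP does not remove the doubt entirely. Its opening to the imputation steps, taken at its word, includes scores missing because of discontinuation for lack of efficacy or an adverse event, since the only exception is protocol-specified worsening. This stands in the primary-analysis section, directly after criteria that say the opposite. SAP 5.5.1 handles missing data at the interim analysis in a similar way to 8.2.1, so the conditional power inherits the ambiguity.

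At stake is whether a programmer following one sentence rather than another credits treatment failures with a missing-at-random chance of response.

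**Working it through.** **Step 1: the rules side by side.** The case is an eye unrescued, meeting no rescue criterion, subject discontinued for lack of efficacy or an adverse event before Month 5, Month 5 VH missing.

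| Source | Result for this eye |
|---|---|
| Protocol 9.1; SAP 2.2.1 | non-responder |
| Protocol 9.5.1, second bullet | imputed, may be a responder |
| Protocol 9.5.1, composite score | -1 |
| Protocol 9.5.2 | silent (rescue criteria only) |
| SAP 5.2.1 and 8.2.1, criterion 2 | non-responder |
| SAP 8.2.1, opening to the imputation steps | imputed, if read literally |
| SAP 8.2.2, LOCF sensitivity analysis | non-responder |

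The rule is explicit in the estimand and in the SAP criteria. It is missing from one protocol bullet and from one SAP sentence.

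**Step 2: the plan's own figure.** Protocol 9.3 gives 30% versus 12%, two-sided alpha 0.05, Pearson chi-square, 80 per arm, 80% power. With the pooled-variance formula and mean rate 0.21:

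n = [1.960 × √(2 × 0.21 × 0.79) + 0.842 × √(0.30 × 0.70 + 0.12 × 0.88)]² / 0.18² = 79.2, rounded up to 80.

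Power at 80 per arm is 80.4%. The figure reproduces and does not depend on the disputed sentence.

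**Step 3: size if the literal wording were followed.** The documents give no discontinuation rate, so these are assumptions:
- 30% and 12% are the estimand rates, with these subjects counted as failures.
- A share d of the arm leaves in this way, without rescue and without meeting a rescue criterion.
- Imputation gives them the response rate of those who stay in their own arm, p/(1-d).
- One eye per subject; the added variance from imputation is ignored.

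The arm's rate becomes p + d × p/(1-d) = p/(1-d). Example with d = 10% in both arms: 0.30/0.90 = 33.3% and 0.12/0.90 = 13.3%, a difference of 20.0 points. That is 8 × 0.333 = 2.7 extra responders per 80 on DE-109 and 8 × 0.133 = 1.1 on sham.

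| d, DE-109 / sham | Rates | Difference (points) | Nominal power |
|---|---|---|---|
| estimand rule | 30.0% / 12.0% | 18.0 | 80% |
| 5% / 5% | 31.6% / 12.6% | 18.9 | 83% |
| 10% / 10% | 33.3% / 13.3% | 20.0 | 86% |
| 15% / 15% | 35.3% / 14.1% | 21.2 | 88% |
| 12% / 6% | 34.1% / 12.8% | 21.3 | 90% |
| 10% / 20% | 33.3% / 15.0% | 18.3 | 78% |
| 2% / 10% | 30.6% / 13.3% | 17.3 | 76% |
| 5% / 15% | 31.6% / 14.1% | 17.5 | 75% |
| 5% / 20% | 31.6% / 15.0% | 16.6 | 70% |

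If VH history halves the imputed rate, the shifts halve: 5%/5% gives 18.5 points, 10%/10% gives 19.0 and 5%/15% gives 17.7.

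**Step 4: direction.** The difference grows only if 0.30 × d/(1-d) on DE-109 exceeds 0.12 × d/(1-d) on sham, that is, if the odds of such dropout on sham are below 0.30/0.12 = 2.5 times those on DE-109. With 5% on DE-109 the odds are 0.0526; 2.5 × 0.0526 = 0.1316, and 0.1316/1.1316 = 11.6%. Sham dropout above that shrinks the difference.

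**The case against.** The strongest reply is that 9.5.1 is not the operative specification. Protocol 9.5 calls itself a summary and defers to the SAP. The SAP is written for the same amendment and states the failure rule twice. The amendment rationale for moving from LOCF to multiple imputation was alignment with the estimands, so a reading that defeats the estimand cannot be intended. This stands. A reader might infer from the 9.5.1 bullet that the planned primary analysis counts treatment failures as responders; the documents do not support that, because SAP criterion 2 assigns them non-response.

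The reply also holds on two further points. Not every unrescued subject is affected, since Protocol 9.5.2 already fails anyone who met a rescue criterion. And a reader might infer a bias towards DE-109, because the arm with the higher response rate gains more per imputed dropout. That holds for equal dropout or more dropout on DE-109, but lack-of-efficacy exits could plausibly be more frequent on sham, and Step 4 shows that this can reverse the sign.

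What does not stand is that the SAP settles everything. The opening to its imputation steps conflicts with its own criterion 2, and the sentence before it can be read either way. SAP 8.2.1 refers to Appendix C for the code, but the contents list stops at Appendix B and no such appendix is in the supplied documents, so code cannot resolve the reading here. SAP section 10 lists only exploratory additions as changes to the protocol and so does not present criterion 2 as replacing the 9.5.1 rule.

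**Conclusion.** The inconsistency is real and concerns the primary endpoint, but it is one of wording. The second bullet of Protocol 9.5.1 contradicts the primary estimand, the composite rule in its own section and SAP criterion 2. The SAP largely closes the gap, while leaving one sentence that repeats it and one that blurs it.

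The consequence is conditional on someone following the literal wording. The difference would then be roughly 17 to 21 points instead of 18, under assumed dropout of 2% to 15% on DE-109 and 5% to 20% on sham. Neither size nor direction can be fixed without dropout rates by arm. No stated figure changes. The treatment policy analysis imputes such missing scores by design and is unaffected.

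This is a minor consistency correction, to be made before unmasking.

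**What to change.** **Protocol 9.5.1, second bullet.** Replace with: *Subjects who discontinue from the study because of lack of efficacy or an adverse event before the visit are non-responders at that visit. Other missing VH scores of subjects not rescued before the visit, and not otherwise classed as non-responders, will be multiply imputed.*

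**SAP 8.2.1, opening to the imputation steps.** Replace with: *For missing VH scores of eyes not classed as non-responders by criteria 1 to 3, multiple imputation will be applied as follows.* Use the same description of the eyes in the sentence before it and in the matching sentence of SAP 5.2.1, keeping the existing provision that scores censored after rescue for other reasons are imputed.

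**Cost.** A few sentences in two documents. No new data, no change to the sample size, and no change to the estimand, which the edits simply carry through.
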